5.2 Trial Treatments

5.2.1 Dose Selection

The rationale for selection of doses and schedules to be used in this trial is provided in Section 4.0 – Background and Rationale. The treatment to be used in this trial is outlined below in Table 2. See Study Flow Chart (Section 6.0) for additional information on treatment schedule.

Table 2 Trial Treatment

Drug	Dose	Dose Frequency	Route of Administration	Treatment Period ¹	Use
Pembrolizumab	200 mg	Once Q3 weeks	IV infusion over 30 minutes	Every 3 week cycle for up to 24 months or 35 cycles (see Section 5.8)	Experimental
GM-CSF	250 µg	Daily on days 1-14 Q3 weeks for 2 cycles	SC**	Two Induction Cycles: Cycles 2 and 3 in Safety Cohort (n=9) and Expansion Cohort (n=15); Cycles 1 and 2 in Efficacy Cohort	Experimental

Key: IV=intravenous; SC=subcutaneous. ¹A subset of patients may be eligible for Second Course pembrolizumab and/or re-induction with GM-CSF (see Section 7.1.5). *Cycle length is 21 days (Q3 weeks) with GM-CSF “induction” in Cycles 2-3 (Safety and Expansion Cohorts) or 1-2 (Efficacy Cohort). **Patients will be instructed on self-injection administration prior to first dose, with re-training each cycle or more often as needed.

5.2.2 Dose Modifications or Interruptions for Toxicity

Toxicity will be assessed according to the NCI CTCAE v4.0. Dose modifications, interruptions, and treatment discontinuation for one or both study drugs will be determined according to the system showing the greatest degree of toxicity and according to the treating investigator's assessment of toxicity attribution. Toxicity will be formally assessed at protocol-defined safety assessment time points well as by investigator review of weekly laboratory testing and, in the interim, by patient contact with the study team. General principles of toxicity management are listed below:

- Laboratory values should be rounded to one significant digit for grade determination according to standard rounding practice.
- Optimal supportive care should be provided for all clinically relevant toxicity.
 - See section 5.6 for guidance on supportive care/rescue medications for specific toxicities.
- Dose interruptions or delays in start of a cycle for any reason (toxicity or non-toxicity) during the Induction Phase (Cycles 1 and 2 in Efficacy Cohort, Cycles 2 and 3 in Safety and Expansion Cohorts) should be applied to both drugs together so that both drugs are restarted on Day 1 of each cycle.

- Doses of GM-CSF which are held during a cycle due to toxicity will not be re-administered.
- Doses of GM-CSF which are missed/skipped (e.g. due to logistical reasons, patient oversight, or other non-toxicity related factors) may be made up at end of cycle, daily for up to 3 doses. Missed/skipped doses >3 will not be re-administered.
- A patient will be removed from protocol therapy if pembrolizumab is permanently discontinued but may continue on pembrolizumab if GM-CSF is discontinued for toxicity before completing induction (2 cycles).
- For any toxicity (regardless of grade), despite optimal supportive care, that is felt by the treating investigator to represent a risk to the patient's safety, additional dose reduction, treatment delay, or treatment discontinuation is permitted at the discretion of the treating investigator.

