5.2.2.2 Dose Modifications for GM-CSF

GM-CSF can induce hematologic effects including variable increases in WBC and/or platelet counts, possibly leading to potential complications of excessive leukocytosis such as hyperviscosity, allergic reactions including anaphylaxis, fluid retention, and respiratory symptoms due to sequestration of granulocytes in pulmonary circulation. Monitoring of blood counts (CBC with differential) is recommended at least twice weekly during GM-CSF administration at standard doses. CBC with differential was checked twice weekly during GM-CSF induction cycles (Cycles 2 and 3) in Safety Cohort. As no increased leukocytosis was observed, weekly testing is performed in the Efficacy and Expansion Cohorts. Liver function and renal function should be monitored at least every 2 weeks on GM-CSF in patients at risk for renal or hepatic dysfunction. Body weight and hydration status should be carefully monitored during GM-CSF administration.

Table 4 Dose Modification Guidelines for GM-CSF-Related Adverse Events

Toxicity	Hold Treatment For Grade	Timing for Restarting*,** Treatment	Discontinue Subject
Leukocytosis	WBC 50,000-100,000/mm ³ and/or ANC > 20,000/mm ³	Hold drug and recheck within 3-7 days; if ANC < 10,000 mm ³ and WBC < 50,000 mm ³ and asymptomatic, re-start with 50% dose reduction (125 µg SQ daily) to complete 14 days; maintain dose reduction for next cycle(s)	If WBC count does not decrease to < 50,000/mm ³ within 3 weeks or recurs >100,000/mm ³ despite 50% dose reduction
	≥ 3 (WBC >100,000/mm ³) and/or hyperviscosity syndrome or complication	Permanently discontinue	Permanently discontinue
Thrombocytosis	Platelet count >500,000/mm ³	Hold drug and recheck within 3-7 days; if platelet count < 500,000/mm ³ and asymptomatic, then re-start with 50% dose reduction (125 µg SQ daily) to complete 14 days; maintain dose reduction for next cycle(s)	If platelet count does not decrease to < 500,000/mm ³ within 3 weeks or recurs >500,000/mm ³ despite 50% dose reduction
	>1,000,000/mm ³ and/or hyperviscosity syndrome or complication	Permanently discontinue	Permanently discontinue
Allergic reactions	3-4	Permanently discontinue	Permanently discontinue

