Edema/fluid retention despite optimal supportive care (e.g. elevation, diuretics)	Moderate or severe (e.g. Grade ≥ 2 if obscuring normal contours or interfering with self-care)	Hold until edema recovers to Grade 0-1 or baseline, then re-start with 50% dose reduction (125 µg SQ daily) to complete 14 days; maintain dose reduction for next cycle(s)	If moderate or severe edema does not recover to Grade 0-1 or baseline within 3 weeks or if recurs despite dose reduction
All other drug-related toxicity ³ attributed to GM-CSF	3 or severe 2	Hold until toxicity resolves to Grade 0-1 or baseline, then re-start with 50% dose reduction (125 µg SQ daily) to complete 14 days; maintain dose reduction for next cycle(s)	Toxicity does not recover to Grade 0-1 or baseline within 3 weeks of last dose
	4	Permanently discontinue	Permanently discontinue

Note: Permanently discontinue for any severe AE that recurs or any life-threatening event.

* Dose interruptions or delays in start of a cycle for any reason (toxicity or non-toxicity) during Induction Phase (Cycles 1 and 2 in Efficacy Cohort (Part 2), Cycles 2 and 3 in Safety and Expansion Cohorts (Parts 1 and 3)) should be applied to both GM-CSF and pembrolizumab together so that both drugs are restarted on Day 1 of each cycle.

**Skipped or missed doses of GM-CSF during a cycle (e.g. due to logistical reasons, patient oversight, or other non-toxicity-related factors) may be made up at end of cycle daily up to 3 doses.

³ Patients with intolerable or persistent Grade <3 drug-related AE may hold study medication at physician discretion. Permanently discontinue study drug for persistent Grade 2 adverse reactions for which treatment with study drug has been held, that do not recover to Grade 0-1 within 3 weeks of the last dose.

Proprietary and Confidential

The information in this document is considered privileged and confidential, and may not be disclosed to others except to the extent necessary to obtain Institutional Review Board approval and informed consent, or as required by federal and state laws. Persons to whom this information is disclosed should be informed that this information is privileged and confidential and that it should not be further disclosed.

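### Rounding laboratory values to one significant digit for grading removes the mandatory GM-CSF stop for WBC 100,001–149,999/mm³

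*Combined protocol and SAP*

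**What the plan says.** Section 5.2.2 opens with general principles that govern both dose-modification tables. One of them is: "Laboratory values should be rounded to one significant digit for grade determination according to standard rounding practice". Grading is by CTCAE v4.0.

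Table 4 in Section 5.2.2.2 has two levels for leukocytosis on GM-CSF:

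- **Hold row.** It applies to a WBC of 50,000 to 100,000/mm³ "and/or ANC > 20,000/mm"³. GM-CSF is held and counts are rechecked in 3 to 7 days. If ANC is below 10,000 and WBC below 50,000, the instruction is "and asymptomatic, re-start with 50% dose reduction". The discontinuation column for this row begins "If WBC count does not decrease to < 50,000/mm"³ and sets a limit of 3 weeks.
- **Permanent-stop row.** It is labelled Grade 3 or higher, defined as "WBC >100,000/mm"³ "and/or hyperviscosity syndrome or complication". GM-CSF is permanently discontinued.

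A note under Table 4 adds: "Permanently discontinue for any severe AE that recurs or any life-threatening event". Section 5.2.2 also says that GM-CSF doses held for toxicity are not given later, and that the investigator may stop treatment for toxicity of any grade.

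On monitoring, Section 5.2.2.2 says of the experience in the Safety Cohort: "As no increased leukocytosis was observed, weekly testing is performed in the Efficacy and Expansion Cohorts".

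**The concern.** The permanent-stop row for leukocytosis is a laboratory grade with a numeric cut-off, which is exactly what the rounding rule covers. One significant digit is very coarse just above a power of ten: the next value after 100,000 is 200,000. A count well above the limit can therefore be rounded down onto the limit, and the limit is a strict inequality.

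The protocol then gives two different actions for one blood result. The cut-off printed in Table 4 makes permanent discontinuation of GM-CSF mandatory. The rounded grade does not, and leaves a conditional hold that can end in a restart at 125 µg. At stake is a safety stopping instruction that sites could apply in different ways.

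The point is limited to this one cut-off. It is unclear whether the rule also reaches limits without a grade label, such as the 50,000 hold limit or the recurrence limit in the hold row, so nothing is claimed about them. Nor is any effect on the Grade 3 or higher safety endpoint claimed.

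**Working it through.** The plan states no figure to reproduce. The check applies the written rule to the written cut-off.

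**Inputs.** Rounding to one significant digit for grading (Section 5.2.2). Grade 3 or higher leukocytosis if WBC > 100,000/mm³, with permanent discontinuation (Section 5.2.2.2, Table 4). Hold row limits: WBC 50,000–100,000/mm³ and/or ANC > 20,000/mm³. Restart limits: WBC < 50,000 and ANC < 10,000 (same table).

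**Step 1: the rounding.** For a WBC in the hundreds of thousands, the value at one significant digit is 100,000 × round(WBC / 100,000).

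- WBC 100,001: 1.00001 rounds to 1, giving 100,000, which is not > 100,000.
- WBC 120,000: 1.2 rounds to 1, giving 100,000, which is not > 100,000.
- WBC 149,999: 1.49999 rounds to 1, giving 100,000, which is not > 100,000.
- WBC 150,000: 1.5 rounds to 2, giving 200,000, which is > 100,000.

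So all 49,999 whole-number counts from 100,001 to 149,999 lose Grade 3 or higher. The result is the same with ties rounded up or to even. It is also the same in units of 10³/mm³, because significant digits do not depend on units. The top of the band is (149,999 − 100,000) / 100,000 = 50% above the limit.

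**Step 2: direction.** Counts of 95,000 to 99,999 round up to 100,000, which still does not exceed 100,000. No count at or below the limit gains the grade, so the error only ever removes the stop.

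**Step 3: other rounding rules, for comparison.**

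| Rule | Counts that lose Grade ≥ 3 | Number of values |
|---|---|---|
| One significant digit (as written) | 100,001–149,999 | 49,999 |
| Two significant digits | 100,001–104,999 | 4,999 |
| Three significant digits | 100,001–100,499 | 499 |
| One decimal place, WBC in 10³/mm³ (assumed units) | 100,001–100,049 | 49 |
| No rounding | none | 0 |

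**Step 4: what applies instead.** The hold row can be reached without rounding any ungraded limit whenever ANC exceeds 20,000. The neutrophil share needed is 20,000 / WBC:

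- at 100,001: 20.0%
- at 120,000: 16.7%
- at 149,999: 13.3%

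If the rounded value of 100,000 is also carried into the hold row, it falls inside the 50,000–100,000 range and no ANC condition is needed.

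**Step 5: what must happen before a restart.** WBC must fall below 50,000, a relative fall of more than 1 − 50,000 / WBC:

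- from 100,001: 1 − 50,000 / 100,001 = 50.0%
- from 149,999: 1 − 50,000 / 149,999 = 66.7%

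The patient must also have ANC below 10,000 and be asymptomatic. The restart is at half dose.

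**The case against.** The strongest answer is that the specific instruction governs the general one. Table 4 prints the absolute count in the row itself, so a site with a WBC of 120,000 can compare it directly with 100,000 and stop GM-CSF without a separate grading step. A sensible site may well do this. But the row is labelled by grade, the rounding rule is written for grading, and nothing in the documents says which prevails. Reading the row unrounded means setting aside a written instruction.

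Second, the wording may be a slip for one decimal place. That is plausible, and it would shrink the band to 49 values if WBC is reported in 10³/mm³. The documents do not say so, and if it is a slip it should be corrected.

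Third, on the narrow reading that rounds only graded limits, a patient with WBC 120,000 and ANC of 20,000 or less fits neither leukocytosis count criterion, so the hold is an inference for that patient. This is fair. It leaves that patient with no clear count-based instruction, which does not help the rule.

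Fourth, other text contains the harm. Hyperviscosity or a complication still forces a permanent stop, as does a life-threatening event or a recurring severe one. Failure to get below 50,000 within 3 weeks ends treatment for a patient in the hold row. Held doses are not made up, induction is two 14-day courses, and the investigator may stop at any grade. No increased leukocytosis was seen in the Safety Cohort. All of this stands and keeps the practical effect small. However, investigator discontinuation is allowed rather than required, and the other permanent stops need something beyond the first count. None restores the mandatory stop for an uncomplicated first count of 100,001 to 149,999.

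**Conclusion.** The concern holds, as a minor one. Followed as written, the rounding rule moves a stated GM-CSF stopping threshold by up to 50% and turns a mandatory permanent stop into, at most, a mandatory hold with a possible half-dose restart. The arithmetic does not depend on reporting units or on how ties are handled. The conclusion rests on two readings: that one significant digit means what it says, and that the rule applies to the graded row of Table 4, from which no text exempts it. The number of patients affected cannot be derived from the documents and is probably very small.

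**What to change.** Delete the rounding sentence in Section 5.2.2, or replace it with a statement that laboratory values are compared as reported with the CTCAE v4.0 and Table 4 limits. If one decimal place was intended, say so and name the reporting units; a band of 100,001–100,049 would then remain for WBC in 10³/mm³. Re-checking grades already recorded is an optional precaution.

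The cost is one sentence in an amendment. Sample size, endpoints and analysis do not change.

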5.2.2.1 Dose Modifications for Pembrolizumab

Adverse events (both non-serious and serious) associated with pembrolizumab exposure may represent an immunologic etiology. These adverse events may occur shortly after the first dose or several months after the last dose of treatment. Pembrolizumab must be withheld for drug-related toxicities and severe or life-threatening AEs as per Table 3 below. As toxicity on pembrolizumab has not been shown to be dose related, dose reductions are not thought to ameliorate specific toxicities. See Section 5.6.1 and Events of Clinical Interest Guidance Document for supportive care guidelines, including use of corticosteroids.

Table 3 Dose Modification Guidelines for Pembrolizumab-Related Adverse Events

Toxicity	Hold Treatment For Grade	Timing for Restarting* Treatment	Discontinue Subject
Diarrhea/colitis	2-3	Hold until toxicity resolves to Grade 0-1	If toxicity does not resolve within 12 weeks of last dose or inability to reduce corticosteroid to 10 mg or less of prednisone or equivalent per day within 12 weeks
	4	Permanently discontinue	Permanently discontinue
AST, ALT, or increased bilirubin (despite optimal supportive care including biliary drainage if obstruction is present)	2 ^{1-3²}	Hold until toxicity resolves to Grade 0-1 or baseline grade (if Grade 2 at baseline) ¹	If toxicity does not resolve within 12 weeks of last dose
	3 ²⁻⁴	Permanently discontinue	Permanently discontinue
Type 1 diabetes mellitus (if new onset) or hyperglycemia	T1DM or 3-4	Hold for new onset Type 1 diabetes mellitus or Grade 3-4 hyperglycemia associated with evidence of beta cell failure; resume pembrolizumab when patients are clinically and metabolically stable	If toxicity does not resolve within 12 weeks of last dose or inability to reduce corticosteroid to 10 mg or less of prednisone or equivalent per day within 12 weeks
Hypophysitis	2-3	Hold until toxicity resolves to Grade 0-1	If toxicity does not resolve within 12 weeks of last dose or inability to reduce corticosteroid to 10 mg or less of prednisone or equivalent per day within 12 weeks
	4	Permanently discontinue	Permanently discontinue
Hyperthyroidism	3	Hold until toxicity resolves to Grade 0-1	If toxicity does not resolve within 12 weeks of last dose or inability to reduce corticosteroid to 10 mg or less of prednisone or equivalent per day within 12 weeks
	4	Permanently discontinue	Permanently discontinue
Hypothyroidism	2-4	Therapy with pembrolizumab can be continued while treatment for the thyroid disorder is instituted	Therapy with pembrolizumab can be continued while treatment for the thyroid disorder is instituted
Myocarditis	Grade 1 or 2	Withhold	Based on severity of AE administer corticosteroids
	Grade 3 or 4	Permanently discontinue	
All other immune-related AEs	Intolerable/ Persistent Grade 2	Withhold	Based on type and severity of AE administer corticosteroids
Infusion reaction	3-4	Permanently discontinue	Permanently discontinue
Pneumonitis	2	Hold until toxicity resolves to Grade 0-1	If toxicity does not resolve within 12 weeks of last dose or inability to reduce corticosteroid to 10 mg or less of prednisone or equivalent per day within 12 weeks
	3-4	Permanently discontinue	Permanently discontinue
Renal failure or nephritis	2	Hold until toxicity resolves to Grade 0-1	If toxicity does not resolve within 12 weeks of last dose or inability to reduce corticosteroid to 10 mg or less of prednisone or equivalent per day within 12 weeks

Proprietary and Confidential

The information in this document is considered privileged and confidential, and may not be disclosed to others except to the extent necessary to obtain Institutional Review Board approval and informed consent, or as required by federal and state laws. Persons to whom this information is disclosed should be informed that this information is privileged and confidential and that it should not be further disclosed.

Toxicity	Hold Treatment For Grade	Timing for Restarting* Treatment	Discontinue Subject
	3-4	Permanently discontinue	Permanently discontinue
All other drug-related toxicity ³ attributed to pembrolizumab	3 or severe 2	Hold until toxicity resolves to Grade 0-1 or baseline grade if abnormal at baseline	If toxicity does not resolve within 12 weeks of last dose or inability to reduce corticosteroid to 10 mg or less of prednisone or equivalent per day within 12 weeks
	4	Permanently discontinue	Permanently discontinue

Note: Permanently discontinue for any severe AE that recurs or any life-threatening event.

* Dose interruptions or delays in start of a cycle for any reason (toxicity or non-toxicity) during Induction Phase (Cycles 1 and 2 in Efficacy Cohort (Part 2), Cycles 2 and 3 in Safety and Expansion Cohorts (Parts 1 and 3)) should be applied to both GM-CSF and pembrolizumab together so that both drugs are restarted on Day 1 of each cycle.

¹ For patients with liver metastasis who begin treatment with Grade 2 AST or ALT, treatment is not required to be held for Grade 2 AST or ALT.

² For patients with baseline Grade 2 AST or ALT, Grade 3 AST or ALT does not automatically require treatment discontinuation. If AST or ALT increases by greater than or equal to 50% relative to baseline and is assessed as treatment-related (e.g. no evidence of interval tumor progression or biliary obstruction) and lasts for at least 1 week despite supportive care, then patients should be discontinued.

³ Patients with intolerable or persistent Grade <3 drug-related AE may hold study medication at physician discretion. Permanently discontinue study drug for persistent Grade 2 adverse reactions for which treatment with study drug has been held, that do not recover to Grade 0-1 within 12 weeks of the last dose. Patients with mild grade 3 toxicity (e.g. mild or asymptomatic rashes or asymptomatic laboratory abnormalities) may be continue on treatment with augmented supportive care and close monitoring at discretion of treating physician.

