5.6 Rescue Medications & Supportive Care

5.6.1 Supportive Care Guidelines for Pembrolizumab

Subjects should receive appropriate supportive care measures as deemed necessary by the treating investigator. Suggested supportive care measures for the management of adverse events with potential immunologic etiology are outlined below and in greater detail in the ECI guidance document. Where appropriate, these guidelines include the use of oral or intravenous treatment with corticosteroids as well as additional anti-inflammatory agents if symptoms do not improve with administration of corticosteroids. Note that several courses of steroid tapering may be necessary as symptoms may worsen when the steroid dose is decreased. For each disorder, attempts should be made to rule out other causes such as metastatic disease or bacterial or viral infection, which might require additional supportive care. The treatment guidelines are intended to be applied when the investigator determines the events to be related to pembrolizumab.

If after the evaluation the event is determined not to be related, the investigator is instructed to follow the ECI reporting guidance but does not need to follow the treatment guidance (as outlined in the ECI guidance document). Refer to Section 5.2.2.1 for guidance on pembrolizumab dose modifications.

Suggested steroid regimens include:

- Systemic steroids equivalent to prednisone 1-2 mg/kg/day for severe immune-related toxicity requiring immunosuppressive therapy.
- Oral prednisone 0.5 mg/kg/day or other equivalent steroid regimen for mild-moderate immune-related toxicity requiring immunosuppressive therapy.
- Topical corticosteroids for mild-moderate dermatitis.
- Corticosteroid eye drops for ocular immune-related toxicity.
- Once symptoms resolve or return to Grade 1/baseline, initiate slow steroid taper over at least 4 weeks, with close monitoring.

It may be necessary to perform conditional procedures such as bronchoscopy, endoscopy, or skin photography as part of evaluation of the event. Suggested conditional procedures, as appropriate, can be found in the ECI guidance document.

- **Pneumonitis:**

- For **Grade 2 events**, treat with systemic corticosteroids. When symptoms improve to Grade 1 or less, steroid taper should be started and continued over no less than 4 weeks.
- For **Grade 3-4 events**, immediately treat with intravenous steroids. Administer additional anti-inflammatory measures, as needed.

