 - **Grade 2** hyperthyroidism events (and **Grade 2-4** hypothyroidism):
 - In hyperthyroidism, non-selective beta-blockers (e.g. propranolol) are suggested as initial therapy.
 - In hypothyroidism, thyroid hormone replacement therapy, with levothyroxine or liothyroinine, is indicated per standard of care.
 - **Grade 3-4** hyperthyroidism events: Treat with an initial dose of IV corticosteroid followed by oral corticosteroids. When symptoms improve to Grade 1 or less, steroid taper should be started and continued over no less than 4 weeks. Replacement of appropriate hormones may be required as the steroid dose is tapered.
- **Hepatitis attributed to immune toxicity:** Assessment should be based upon greatest increase in AST, ALT, or total bilirubin. Elevations in alkaline phosphatase alone should not be used to determine treatment-related toxicity grade or supportive care interventions since this marker is commonly elevated in biliary tract cancers and may be an index of biliary obstruction independent of treatment-related toxicity. Evaluation for viral reactivation and antiviral therapy for HBV or HCV should be considered if any evidence hepatotoxicity according to standard institutional practice in HBV/HCV patients receiving anti-cancer therapies
 - For **Grade 2** events (if normal or Grade 1 at baseline), monitor liver function tests more frequently until returned to baseline values (consider weekly) to ensure not progressive.

- For **Grade 4** events and **Grade 3** if increased by greater than or equal to 50% relative to baseline and is assessed as treatment-related (e.g. no evidence of interval tumor progression or biliary obstruction), treat with intravenous corticosteroids for 24 to 48 hours.
- When symptoms improve to Grade 0-1 or baseline, a steroid taper should be started and continued over no less than 4 weeks.
- **Renal failure or Nephritis:**
 - For **Grade 2** events assessed as treatment-related and despite best supportive care (e.g. oral or IV hydration), treat with oral or systemic corticosteroids.
 - For **Grade 3-4** events, treat with systemic corticosteroids.
 - When creatinine value improves to Grade 1 or less, steroid taper should be started and continued over no less than 4 weeks.
- **Other immune-mediated adverse reactions, including ocular manifestations**
 - Permanently discontinue pembrolizumab if clinically significant or severe immune-mediated adverse reactions (see 5.2.2.1).

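### Table 3 puts treatment-related Grade 3 bilirubin under both hold-and-restart and permanent discontinuation, and its footnotes separate the two actions for AST/ALT only

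*Combined protocol and SAP*

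**What the plan says.** Section 5.2.2.1 makes Table 3 binding for pembrolizumab-related toxicity. The table handles three liver measures in one row: "AST, ALT, or increased bilirubin (despite optimal supportive care including biliary drainage if obstruction is present". The row has two lines.

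- **Hold line.** The restart condition is "Hold until toxicity resolves to Grade 0-1 or baseline grade (if Grade 2 at baseline". The last column stops treatment if the toxicity has not resolved within 12 weeks of the last dose.
- **Discontinuation line.** Pembrolizumab is stopped permanently.

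Two footnotes belong to this row. Footnote 1 concerns patients with liver metastasis who start with raised enzymes, for whom "treatment is not required to be held for Grade 2 AST or ALT". Footnote 2 says: "For patients with baseline Grade 2 AST or ALT, Grade 3 AST or ALT does not automatically require treatment discontinuation". It then gives the circumstances in which those patients do stop, beginning "If AST or ALT increases by greater than or equal to 50% relative to baseline" and adding that the rise must be judged treatment-related and last at least a week despite supportive care.

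Section 5.6.1 covers immune hepatitis. It states: "Assessment should be based upon greatest increase in AST, ALT, or total bilirubin". Its instructions there concern monitoring and corticosteroids. For holding or stopping the drug it sends the reader back: "Refer to Section 5.2.2.1 for guidance on pembrolizumab dose modifications".

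**The concern.** If both lines include Grade 3, a reader who follows the table literally finds two actions for one event. Under one, the patient may resume pembrolizumab after recovery. Under the other, pembrolizumab ends, and Section 5.2.2 then removes the patient from protocol therapy. A footnote that names only AST and ALT cannot resolve this for bilirubin, although bilirubin is in the same row.

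What is at stake is equal handling of the same safety event in different patients. Section 8.3.2 also lists treatment delays and discontinuation for lack of tolerability among the quantities to be reported. If the line chosen varies from case to case, those figures partly reflect how the table was read.

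**Working it through.** No arithmetic underlies the point itself; it is a comparison of texts.

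**Step 1: the grades in each line.** In the text copy the superscripts in the two hepatic grade cells are damaged. The most plausible reading is 2¹-3² for the hold line and 3²-4 for the discontinuation line. Three things support it:
- Table 3 has no footnote 4, so the 4 must be a grade.
- Footnote 1 is about Grade 2 and footnote 2 about Grade 3, which matches where they sit.
- The hold line allows recovery to a Grade 2 baseline. That makes sense only if the line includes events above Grade 2.

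Hold = {2, 3}; discontinue = {3, 4}; overlap = {3}.

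**Step 2: the other rows.** Every other row of Table 3 with two lines separates its grades (hold / discontinue):
- diarrhea/colitis 2-3 / 4
- hypophysitis 2-3 / 4
- hyperthyroidism 3 / 4
- myocarditis 1-2 / 3-4
- pneumonitis 2 / 3-4
- renal 2 / 3-4
- all other drug-related toxicity 3 or severe 2 / 4

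Only the hepatic row overlaps.

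**Step 3: what resolves the overlap.**
- *AST/ALT, Grade 2 at baseline:* footnote 2 says Grade 3 does not stop treatment automatically and gives the conditions under which it does.
- *AST/ALT, other patients:* the exception implies that Grade 3 falls in the discontinuation line. This is not stated, but it is the ordinary reading of a rule with an exception.
- *Bilirubin:* neither footnote mentions it. Footnote 3 belongs to the row for all other drug-related toxicity. The note under the table stops treatment for a severe event that recurs or any life-threatening event; that settles a repeat Grade 3 event but not a first one. Section 5.6.1 counts bilirubin in the grading but returns the reader to Section 5.2.2.1.

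**Step 4: where the two lines end differently.** If Grade 3 bilirubin does not resolve within 12 weeks, both lines end in discontinuation. If it resolves in time, one line permits restart and the other forbids it. The conflict lies there.

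**Step 5: reach.** Section 1.0 gives 9 + 18 = 27 patients in completed Stages 1 and 2, and 42 - 27 = 15 in the Expansion Cohort. Stage 2 enrollment finished in September 2017 (Section 8.4.5) and this version is dated 10/01/2019, about 24 months later. Planned treatment is up to 24 months or 35 cycles, so few earlier patients can still be on a first course.

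No rate of Grade 3 bilirubin is given. The nearest figure is in Section 8.4.4: 11% of the Safety Cohort, consistent with 1/9, had any at least possibly related event of Grade 3 or higher in the first three cycles. On that reading at most one of those nine had the event in question, over 9 weeks only.

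**The case against.** The best answer is that the overlap is deliberate. Both 3s carry footnote 2, so the table signals that Grade 3 is split by a condition. The exception for baseline Grade 2 AST/ALT has meaning only if Grade 3 otherwise leads to discontinuation, and bilirubin, being outside the exception, would stay under that general rule. Table 1 suggests why only the enzymes are named: it admits AST and ALT up to 5 times the upper limit of normal, but total bilirubin only to 1.5 times, or above that if direct bilirubin is normal.

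For AST/ALT this argument stands. A reader might infer that the whole row contradicts itself; footnote 2 does not support that. For bilirubin it remains an inference. The row names bilirubin and lists Grade 3 under hold without limiting that entry to the enzymes. Section 5.6.1 also points the other way: it grades on the worst of the three measures and divides Grade 3 by a 50% rise from baseline, without confining this to AST/ALT. A reader could equally suppose that Grade 3 bilirubin was meant to be divided too.

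Four points on scale also stand:
- The row applies only to events attributed to pembrolizumab that persist despite drainage, so obstructive rises judged unrelated fall outside it.
- Patients are treated at one institution, and Appendix 11.1 has a monthly committee review of Grade 3-5 events. This limits inconsistency but does not say which line governs.
- Patients who stop without progression remain under disease follow-up (Section 5.8), so outcome assessment continues.
- The grade cells are reconstructed and should be confirmed against the source table.

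**Conclusion.** The point holds for bilirubin. On the most plausible reading of the grade cells, treatment-related Grade 3 bilirubin that persists despite drainage is assigned both to hold-and-restart and to permanent discontinuation, and nothing in the documents chooses between them. For AST/ALT, footnote 2 works as an exception with its general rule implied; that could be clearer but is not a contradiction.

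The effect is on consistent safety management and the reported discontinuation rate. It falls mainly on the 15 Expansion Cohort patients and on any earlier patients still on treatment or returning for a Second Course. A reader might extend it to all 42 patients, but 27 were in stages already fully enrolled. A reader might also look for an effect on power or sample size; there is none, and for efficacy only exposure could change. Nor do the documents show that Section 5.6.1 conflicts with Table 3, since it defers to that table. The number of events is not stated and is likely to be small. The case for correction rests on a binding safety table giving opposite actions for one event.

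**What to change.** The sponsor should reconcile the two hepatic lines of Table 3 and footnote 2 so that each grade of AST/ALT, and separately each grade of bilirubin, falls under one action, with any dependence on baseline grade stated for each measure. The general rule that footnote 2 now implies for AST/ALT should be written out. The hepatitis text in Section 5.6.1 should then be checked for consistency. Which action applies to Grade 3 bilirubin is for the sponsor and its safety team; this review takes no position.

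The cost is a clarifying amendment to one table row and a footnote, with the protocol committee and IRB approval that Section 10.4 requires. It has no statistical cost.
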